9.3.2 Exposures

The definition of drug exposure for Empagliflozin will be any patient using at least one prescription of Empagliflozin tablets (10 or 25 mg) or fixed-dose combinations with metformin. For the comparator group, the patients will have at least one prescription of DPP-4 inhibitors. DPP-4 inhibitor users included in this study will be using one of the following approved drugs in Saudi Arabia: Sitagliptin, Saxagliptin, Vildagliptin, Alogliptin, Linagliptin, or fixed-dose combinations of these drugs with metformin. [R17-3427]

Furthermore, each member of the population exposed to Empagliflozin must have at least one prescription for Empagliflozin, with or without other glucose-lowering drugs (GLDs), and have no prior prescriptions of a DPP-4 inhibitor or Empagliflozin during the available pre-index period. Each member of the population exposed to a DPP-4 inhibitor must have at least one prescription for a DPP-4 inhibitor, with or without other GLDs, and no prior prescriptions of a DPP-4 inhibitor or Empagliflozin during the available pre-index period.

Add-on therapy will be allowed after using the exposure of interest as the initial drug for new users. Therefore, using the drug as part of dual therapy or triple therapy will be allowed.

The use of studied medications will be defined on different levels: current use, recent use and discontinuation of the studied drugs. Current use of the index drugs will be defined from the date of prescription of Empagliflozin or DPP-4 inhibitor to the end of supply for that prescription plus a period of 30 days. Recent use will be defined from the end of current use (30 days after end of supply) until 90 days later (which is 120 days after end of supply).

Discontinuation of the index drug will be defined as no further prescription 120 or more days after the end of the last prescription's supply. Patients who discontinue an index drug and then subsequently initiate another index drug will not be allowed to re-enter the study.

Patients switching to or adding Empagliflozin to other antidiabetic medications will be compared to patients switching to or adding comparator treatment on the same background therapy. Identification of a "new-user" design is an appropriate method for studying second-line therapies in chronic conditions.

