During the statistical analyses, analyses will be stratified by treatment complexity (mono vs. dual vs. triple therapy) and by calendar time of treatment initiation. Prior or current use of insulin is allowed; an additional stratified analysis by insulin use is planned. Propensity scores based on information prior to the index date will be used to account for potential confounding.

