9.7.1 Propensity score modelling

A propensity score (PS) method will be utilized to control for confounding in the analysis phase. It is used to balance the baseline covariates predictive of treatment, to lessen the unequal chance of receiving Empagliflozin versus DPP-4 inhibitors. PS will be estimated with logistic regression for each cohort member. PS is one of effective methods used in epidemiological studies analyses.

Bivariate analysis will be initially used for the selection of potential clinical covariates for inclusion in the propensity score model. Demographic and clinical categorical data will be analysed using an χ^2 or Fisher's exact test while continuous variables will be analysed using a student's t-test or Mann-Whitney U test.

The model will be selected in a process optimizing the goodness of fit. Only clinically relevant, statistically significant (p-value <0.25) covariates will be included. Propensity

[figure not shown]
scores will be stratified into quintiles, and subsequent covariate balance will be reviewed graphically and with Mantel-Haenszel tests.

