4.9 Analyses

For descriptive analysis of parameters, see section 4.7 above. In the following, analysis of the endpoints is described in detail.

The effect of exposure to EMPAGLIFLOZIN on the risk of ketoacidosis, severe urinary tract infections, volume depletion and dehydration compared to those exposed to DPP-4 inhibitor will be estimated. Hence, the following is applied to each of the four outcomes of interest.

The endpoints will be analysed in the index period (primary), in the index period during Ramadan (secondary), in the follow-up period and in the follow-up period during Ramadan.

Estimation of propensity scores

In a preparatory step, for each patient, propensity scores (PS) will be estimated by means of logistic regression, estimating the likelihood of a patient receiving Empagliflozin based on prior and baseline confounders predictive of treatment. The statistical model will be built by a selection process optimizing the goodness of fit.

At first, the relationship between treatment (EMP, DPP-4 inhibitor) and all potential clinical confounder candidates will be tested in bivariate analyses. Based on the type of the candidate, Fisher's exact tests or Student's t-tests will be applied [Heiberger 2015]. In case of distributional constraints, χ^2 tests or Mann-Whitney U tests may be alternatively applied, respectively.

Clinically relevant confounder candidates include age, gender, body mass index (BMI), blood pressure, fasting blood glucose level at baseline, and baseline HbA1c, if available, comorbidity indicators like hypertension, dyslipidaemia, kidney diseases, kidney stones, history of kidney transplant, liver diseases, prostate diseases, pancreatitis, surgery, infections (other than UTIs) and heart diseases, if available, genital defects, urinary tract anatomical defects, laboratory measurements and relevant prior and concomitant medications at baseline. Relevant prior medications in the last 6 months and at baseline include insulin sulfonylureas, meglitinides, thiazolidinediones, α -glucosidase inhibitors, glucagon-like peptide-1 receptors, antihyperlipidemics (statins, fibrates, niacin), antihypertensive agents (diuretics, ACE inhibitors, beta blockers), antipsychotic medications, corticosteroids, tacrolimus, glucagon, interferon,

Statistical Analysis Plan (SAP)

Document Date: 17APR2019

Document Version: 1.0 Final

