albuterol, dopamine, dobutamine, terbutaline and ritodrine. However, candidates cannot be considered if unknown or missing in a significant number of patients.

If the p-value of bivariate analysis is lower than 0.25, confounder candidates will be included in an initial multivariate logistic regression model. By backward elimination, or other appropriate methods of model selection, the model will be optimized to yield a final model.

The resulting PS will be described by group by means of a summary table. The distribution of the PS will be plotted for the two treatment groups (EMP, DPP-4 inhibitors) to see whether there are any areas where there is no overlap. The estimates of treatment effect may not be reliable in areas where there is no overlap. The area with overlap is called the common support region. It may be necessary to remove subjects outside of the common support region (e.g. extreme tails of the PS distribution) before analysis.

The effect of the confounders in bivariate testing and in the initial and final models will be described by p-values.

PS-based Analysis

Based on those PS, the main analysis approach is stratification to control for confounders,

The stratification will divide the entire study population into five groups by PS quintiles based on their PS value. Quintiles will be used for analysis if the number of patients are sufficiently balanced per group within strata and if the confounding covariates are balanced. Balance will be reviewed graphically and, depending on the scale of the covariate, by Mantel-Haenszel and other applicable tests of confounding covariates of the final model by strata. If, due to significantly low p-values from Mantel-Haenszel and other applicable tests, the balance based on quintiles is insufficient, the number of strata will be increased. Balance investigations will be repeated and the number of strata further increased until a reasonable degree of balance is achieved. It may also be necessary to remove patients from extreme tails of the PS distribution.

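### Propensity covariates are selected by p-value against treatment, and the SAP candidate list does not name several background-therapy and severity variables the protocol collects, so these can go unadjusted and unchecked

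*SAP*

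**What the plan says.** SAP 4.9 builds the score in two data-driven steps. First, "the relationship between treatment (EMP, DPP-4 inhibitor) and all potential clinical confounder candidates will be tested in bivariate analyses", and the entry rule is "If the p-value of bivariate analysis is lower than 0.25, confounder candidates will be included in an initial multivariate logistic regression model". Then: "By backward elimination, or other appropriate methods of model selection, the model will be optimized to yield a final model". The declared aim is goodness of fit. No retention threshold is given and no covariate is mandatory. Protocol 9.7.1 has the same screen: "Only clinically relevant, statistically significant (p-value <0.25) covariates will be included".

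Balance across strata is judged by "tests of confounding covariates of the final model by strata". If it is poor, the number of strata is increased.

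The SAP candidate list covers age, sex, BMI, blood pressure, glucose, HbA1c, a set of comorbidities, laboratory values and drugs. Its glucose-lowering part begins: "Relevant prior medications in the last 6 months and at baseline include insulin sulfonylureas, meglitinides, thiazolidinediones". It goes on to alpha-glucosidase inhibitors and the GLP-1 class. Metformin, add-on versus switch, treatment complexity, diabetes duration and prior ketoacidosis are not named.

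Protocol 9.3.2 says that patients switching to or adding empagliflozin "will be compared to patients switching to or adding comparator treatment on the same background therapy", and that "analyses will be stratified by treatment complexity (mono vs. dual vs. triple therapy) and by calendar time of treatment initiation". Protocol 9.3.4 defines index-date indicators for add-on versus switch and for mono, dual or triple therapy. It treats disease duration as a severity measure and lists prior ketoacidosis (variable 46) and metformin (variable 78). Visit 1 (9.2.2.1) records the diagnosis date, prior anti-hyperglycaemic agents and a history of ketoacidosis.

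**The concern.** A propensity score controls confounding by balancing outcome risk factors. A rule that looks only at association with treatment can drop a strong risk factor with a modest imbalance and keep a variable that predicts treatment but not outcome. It also makes the adjustment set depend on the data, with room for analyst choice in the elimination step.

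The unlisted variables matter more. Background therapy and disease duration plausibly differ between new users of the two classes, and prior ketoacidosis bears directly on one primary outcome. If they are not offered to the model, nothing limits their imbalance. The balance check would not show it either, because it covers only final-model covariates. SAP Table 15.17 does plan standardised differences, but its title confines them to propensity-score confounders.

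**Working it through.** The documents give no figure to reproduce here. The only size figure is 2 × 750 = 1,500, set by the regulator. Prevalences and risk ratios below are assumptions.

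**1. What the screen lets through.** With 750 per group, a covariate fails at p<0.25 when its observed standardised difference is below 1.150 × √(2/750) = 0.059. If elimination used p<0.05 (assumed; none is stated), the limit is 1.960 × √(2/750) = 0.101.

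**2. Bias from an omitted binary covariate.** With prevalence p1 (empagliflozin) and p0 (DPP-4 inhibitor) and outcome risk ratio RR, the incidence rate ratio is multiplied by (1 + p1(RR−1)) / (1 + p0(RR−1)).

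**3. Bias due to the screen alone.** The imbalance that counts is the one present in the sample, given that the covariate failed the screen.

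| Assumed case (empagliflozin v DPP-4i) | P(fails), normal approx. | P(fails), Fisher | Mean factor given failure, chi-square / Fisher |
|---|---|---|---|
| 1% v 2%, RR 10 | 0.33 | 0.40 | 0.975 / 0.968 |
| 15% v 18%, RR 4 | 0.34 | 0.36 | 0.981 / 0.979 |

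The average bias is therefore about 2–3%. In one million simulated samples with a chi-square-type screen the factor never fell below 0.934 and 0.957, so the bias was at most about 4–7%. Under Fisher's test the most extreme failing tables reach about 0.92 and 0.95.

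The largest imbalances that still fail Fisher's test, taking fixed DPP-4 inhibitor counts:
- 8 v 14 patients: 1.03 (RR 5) to 1.07 (RR 10).
- 38 v 49 patients: 1.05 to 1.09.

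**4. If elimination used p<0.05 (assumed).** 38 v 57 patients could be dropped, with factors 1.08 (RR 5) to 1.16 (RR 10).

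**5. A variable never offered to the model.** No test bounds its imbalance.
- 30% v 50% (DPP-4i v empagliflozin): RR 2 gives 1.5/1.3 = 1.15; RR 3 gives 2.0/1.6 = 1.25.
- 30% v 60%: RR 2 gives 1.6/1.3 = 1.23; RR 3 gives 2.2/1.6 = 1.38.

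**6. Can the outcome model make up for it?** SAP 4.9.1 says these models will contain covariates with a potential effect on outcome. The listed candidates are optional, further effects are still to be short-listed, and only the index quarter is fixed. The models are fitted within strata of about 1,500/5 = 300 patients, and protocol 9.9 concedes that numbers may be low for ketoacidosis. This route may help, but the plan does not guarantee it.

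**The case against.** **The list is open.** SAP 4.9 gives examples and refers to relevant prior and concomitant medications, so metformin and prior ketoacidosis could be read in. Protocol 9.3.4 says only that variables will be considered for the score. This stands: the five variables may be adjusted for, but nothing ensures it.

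**The SAP may appear to break the protocol's stratification commitment.** A reader might infer this because SAP 4.9.4 treats complexity as a descriptive subgroup. The documents do not settle it. The protocol sentence stands next to a planned stratified analysis by insulin use and can mean subgroup analyses, and SAP 4.9.4 repeats the analyses within complexity, insulin and metformin subgroups. SAP 4.9.3 and part of 4.10 are not legible in the public copy, so no unexplained departure can be claimed. The p<0.25 rule itself is common to both documents.

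**The screen may appear to do large damage.** A reader might apply the true imbalances (1.09/1.18 = 0.92 and 1.45/1.54 = 0.94) and stack three omissions to 0.94³ = 0.83. That is not supported. A covariate that fails the screen has a small observed imbalance, so three at 0.981 give 0.981³ = 0.94. Three independent failures would have probability of only about 0.33³ = 0.04.

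**Forcing covariates in has a cost.** HbA1c and renal function are recorded if available, and SAP 4.8 rules out imputation. An ordinary logistic model would lose every patient with a gap. This is right, and the fix has to deal with it.

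**Conclusion.** The point holds as a weakness in prespecification. Followed as written, the plan can leave metformin, add-on versus switch, treatment complexity, diabetes duration and prior ketoacidosis unadjusted in the main analysis, and its balance check would not reveal this. It does not follow that they will be unadjusted, or that all four outcomes would be affected alike.

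The p<0.25 screen contributes little: about 2–3% on average in the two examples, and no more than about 9% in any case tried with a risk ratio up to 10. The open elimination step could add to that. The main exposure is from variables never offered, at 1.15 to 1.25 for 30% versus 50% and risk ratios of 2 to 3. All these sizes rest on assumed prevalences and risk ratios, and they ignore partial adjustment through correlated covariates such as insulin or sulfonylurea use. Insulin and the other named drug classes are candidates already, and the index quarter is fixed in the outcome model. The change is worth making because it is cheap and the variables are already provided for.

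**What to change.** In SAP 4.9 and protocol 9.7.1, replace the p-value screen and the elimination step with a prespecified covariate set chosen on outcome risk:

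- age, sex, BMI and blood pressure;
- insulin, metformin, treatment complexity and add-on versus switch;
- diuretics and other antihypertensives;
- diabetes duration, prior ketoacidosis, and renal and urinary-tract history;
- HbA1c and eGFR, with a missing category or indicator so that no patient leaves the analysis.

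State the missing-data rule in SAP 4.8 and apply it to any other member of the set that may be unrecorded. Keep the index quarter as SAP 4.9.1 has it. Judge the score by standardised differences within strata for the whole set, rather than by goodness of fit or by tests on retained covariates only.

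The cost is document wording, a somewhat larger propensity model and the added missing-data rule. No new data collection is needed.

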9.7 DATA ANALYSIS

Details of all analyses and variables specification will be defined in a separate SEAP.

Patients are grouped according the exposure to either Empagliflozin or DPP-4 inhibitors. Data will be analysed per group. Let the index period define the time from index date to the end of treatment as defined in [section 9.3.2](#) by current use, and the follow-up period the time from index date to the end of observation as defined in [section 9](#). Incidences will be derived if events of interest occur in the respective period. The main analysis will consider index periods only, a secondary analysis will consider only the time of the index period in the month of Ramadan in every year, while sensitivity analyses will consider respective follow-up periods, overall or during Ramadan only. Times from index date to first occurrence will also be determined per event of interest and described by means of Kaplan-Meier estimates and median times with 95% confidence intervals, where appropriate.

All individual data will be listed and described per group by means of summary tables presenting frequency counts and percentages for categorical data and arithmetic means, standard deviations, medians, minimum and maximum values for continuous data. Baseline is defined as the last observation on or before the index date.

For the assessment of the primary and secondary objectives, the main data analysis will be conducted in two stages:

- 1) Construction of the PS by modelling the exposure to Empagliflozin vs. DPP-4 inhibitor;
- 2) Estimation of the effect of exposure to Empagliflozin on the risk of ketoacidosis, severe urinary tract infections, volume depletion and dehydration compared to those exposed to DPP-4 inhibitor.

Propensity score stratification will be the primary method to control for the confounders in the analysis phase. The stratification will divide the study population in several groups (max. 5 groups) based on their propensity score value. Propensity score matching will also be used as secondary method in the analysis phase.

All statistical tests will be conducted with a two-sided significance level alpha of 0.05 and all analyses will be conducted using SAS statistical analysis software version 9.4 (SAS Institute, Inc., Cary, NC) or later.

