15.17	Diabetic Ketoacidosis: PS Confounders Summary – Standardized Differences and p-values
15.18	Diabetic Ketoacidosis: Stratified IRR Analyses, Index Period
15.19	Diabetic Ketoacidosis: Stratified IRR Analyses, Index Period during Ramadan
15.20	Diabetic Ketoacidosis: Stratified IRR Analyses, Follow-up Period
15.21	Diabetic Ketoacidosis: Stratified IRR Analyses, Follow-up Period during Ramadan
15.22	Diabetic Ketoacidosis: Stratified PH Analyses of Time to First Occurrence in Index Period
15.23	Diabetic Ketoacidosis: Stratified PH Analyses of Time to First Occurrence in Index Period during Ramadan
15.24	Diabetic Ketoacidosis: Stratified PH Analyses of Time to First Occurrence in Follow-up Period
15.25	Diabetic Ketoacidosis: Stratified PH Analyses of Time to First Occurrence in Follow-up Period during Ramadan
16.1-25	same 25 outputs for severe UTI
17.1-25	same 25 outputs for volume depletion
18.1-25	same 25 outputs for dehydration

Statistical Analysis Plan (SAP)

Document Date: 17APR2019

Document Version: 1.0 Final

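### Propensity-score strata are added on the basis of low p-values, with no limit on the size of imbalance and no maximum number of strata

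*SAP*

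**What the plan says.** SAP 4.9, under the PS-based analysis: "The stratification will divide the entire study population into five groups by PS quintiles based on their PS value". Quintiles are kept if patient numbers per group are adequate within strata and the covariates are balanced. On how balance is judged: "Balance will be reviewed graphically and, depending on the scale of the covariate, by Mantel-Haenszel and other applicable tests". These tests apply to the covariates of the final propensity model, by strata. Balance is called insufficient "due to significantly low p-values from Mantel-Haenszel and other applicable tests", and strata are then added: "Balance investigations will be repeated and the number of strata further increased until a reasonable degree of balance is achieved". Patients in the extreme tails of the score may also be removed.

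SAP 4.6 sets a default significance level of 0.05, and no other level is given for the balance tests. Standardised differences appear only in a table title in SAP 5.1 (Table 15.17, repeated for the other outcomes): "Standardized Differences and p-values". No threshold or decision is attached to them.

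The protocol takes a similar approach to checking balance. In 9.7.1, "subsequent covariate balance will be reviewed graphically and with Mantel-Haenszel tests". On the number of strata, 9.7 says "The stratification will divide the study population in several groups (max. 5 groups) based on their propensity score value", and 9.7.1 and 9.7.2 use quintiles. The abstract (section 4, Data analysis) instead adjusts for deciles of the score together with calendar year.

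**The concern.** Stratification on the propensity score is the main control of confounding in a non-randomised safety comparison, so the rule that fixes the strata is part of the primary analysis. The only stated trigger for changing them is a significance test. A test result depends on the number of patients, the number of tests and chance as well as on imbalance. The measure that does express the size of imbalance will be reported but does not govern anything.

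The wording also leaves open whether each covariate is tested once across strata or separately in every stratum. The two readings lead to opposite behaviour, and neither follows the size of the imbalance.

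Needless strata carry a cost. SAP 4.9.1 fits logistic and Cox models within each stratum and averages the results, and protocol 9.9 concedes that patient numbers may be too low to assess ketoacidosis. A stratum with no events in one group gives no finite ratio estimate.

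**Working it through.** The documents state no balance threshold or target number of strata beyond those above, so there is no figure of theirs to reproduce.

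**Inputs from the documents.** 1,500 patients, aimed at 750 per cohort (SAP 4.2); two-sided 0.05 (SAP 4.4, 4.6); five strata to start (SAP 4.9). With equal cohorts and equal split this is 1,500/5 = 300 patients per stratum, or 150 per cohort; ten strata give 75 per cohort.

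**1. Same imbalance, different verdict.** For standardised difference d and n patients per cohort, the standard error is √(2/n) and z = d/√(2/n).

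- n = 150: √(2/150) = 0.115; d = 0.10 gives z = 0.87, p = 0.39.
- n = 750: √(2/750) = 0.0516; d = 0.10 gives z = 1.94, p = 0.053.
- n = 3,000: √(2/3,000) = 0.0258; d = 0.10 gives z = 3.87, p = 0.0001.

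The difference that just reaches p = 0.05 is 1.96 × √(2/n): 0.10 at 750 per cohort, 0.23 at 150 and 0.32 at 75.

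**2. Behaviour of the rule.** Simulation assumptions, not taken from the documents: N = 1,500; 10 independent normal covariates, all in the propensity model; log-odds of 0.15 or 0.30 each; 200 runs per setting. The within-stratum test compares cohort means in each stratum. The pooled test uses z = Σw·d / √(Σw·s²), where d is the stratum mean difference, s² the stratum variance and w = n₁n₀/(n₁+n₀).

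| Strata | Runs with any within-stratum p<0.05 | Runs with any pooled p<0.05 | Mean of largest pooled standardised difference |
|---|---|---|---|
| 5 | 82-87% | 0 of 200 | 0.026-0.047 |
| 10 | 97-99% | 0 of 200 | 0.016-0.034 |
| 20 | 100% | 0 of 200 | 0.016-0.035 |

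A separate simulation, also with N = 1,500 and 10 covariates in the model, gave 72-90% at 5 strata, 98% at 10 and 100% at 20 for the within-stratum tests, and again no significant pooled test. Together these give about 70-90% at quintiles and 97-100% at 10 to 20 strata.

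**3. Cost of extra strata.** Assume e events in each cohort, each equally likely to fall in any of K strata. The expected share of strata with events in both cohorts is (1 − (1 − 1/K)^e)².

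- 10 events in total (e = 5): K = 5 gives (1 − 0.8⁵)² = 45%; K = 10 gives (1 − 0.9⁵)² = 17%.
- 20 events in total (e = 10): K = 5 gives (1 − 0.8¹⁰)² = 80%; K = 10 gives (1 − 0.9¹⁰)² = 42%.

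**The case against.** The best defence is that Mantel-Haenszel, the only test named, pools over strata, and that the tests cover covariates already in the propensity model. Stratifying on the score pushes those covariates towards balance, so pooled tests reject far less often than 5% of the time. The simulations bear this out, including at N = 6,000. On this reading quintiles would almost always stand and no harm follows. That is correct, but the rule is then nearly inert. It also says nothing about covariates dropped during model selection, because only those in the final model are tested.

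The SAP is also not a pure p-value stop. It names graphical review, asks for adequate patient numbers per group within strata, and words the end point as an acceptable degree of balance. This stands as far as it goes, but none of these carries a criterion, and low p-values remain the only stated reason for calling covariate balance insufficient.

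SAP 4.9.1 allows outcome models to include the confounder candidates, and protocol 9.7 plans matching as a secondary method. Both soften the consequence of imperfect strata. Neither fixes how many strata there are.

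Two stronger inferences fail. A reader might expect the loop to end because small strata lack power. Power to flag a difference of 0.20 in one stratum does fall, from 41% at 150 per cohort to 23% at 75, but the number of tests grows with the strata, and the chance of at least one low p-value rises. A reader might also apply 1 − 0.95ᵏ to k pooled tests. That assumes independent tests rejecting at 5% each, which does not hold for covariates in the score.

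**Conclusion.** The point holds as a weakness in a pre-specified decision rule. The stated trigger does not measure imbalance, the end point is undefined and the SAP sets no maximum. If tests are read within strata, strata would be added in most runs at quintiles and the loop need not end, even with pooled differences averaging below 0.05. If tests are pooled, the rule almost never acts on covariates in the score.

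The percentages rest on the simulation assumptions above, and the sparse-event figures on the assumed even spread of events. The p-values for a difference of 0.10 need only the planned cohort sizes, equal splitting and the normal approximation.

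Two further conclusions are not supported. The work does not show that residual confounding would be wrongly declared resolved, since pooled imbalance at quintiles was small in these simulations. Nor can the SAP simply be said to breach a settled limit of five strata: the protocol's body and abstract disagree, SAP 4.10 is partly redacted and SAP 4.9.3 is not in the text available, so nothing is inferred from their silence.

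**What to change.** In SAP 4.9:

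- Replace the p-value trigger with a pre-specified limit on the absolute standardised difference pooled over strata. A value of 0.1 would serve, stated as a convention for the sponsor to justify, since the documents give none. In the simulation at N = 1,500, quintiles met it on average without added strata.
- Show within-stratum differences descriptively only. At 150 per cohort their chance standard error is about 0.115, so a limit of 0.1 applied there would again be driven by chance.
- If a covariate exceeds the limit, respecify the propensity model (interactions, non-linear terms) or adjust for that covariate, in place of adding strata without end.
- Reconcile the protocol's limit of five groups and its quintiles (9.7, 9.7.1, 9.7.2) with the deciles and calendar year in its abstract, then state one fixed maximum number of strata.
- Lock the propensity model and strata before outcomes are examined.

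The cost is wording in the SAP, plus the reconciliation of the protocol passages. No new data are needed, and the standardised differences are already planned for Table 15.17.
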